PROTOCOL SYNOPSIS

Study Title	Randomized Clinical Trial to Evaluate the Efficacy of Bifidobacterium BB-12® in the Treatment of Infantile Colic
Protocol no.	PSC-DS BIGI
Sponsor	SOFAR S.p.A.
Name of finished product	Bifidobacterium BB-12®
Investigators and study centers	[name] [name] Dipartimento di Scienze Mediche Traslazionali – Sezione Pediatrica Laboratorio Europeo per lo Studio delle Malattie Indotte da Alimenti Università degli Studi di Napoli “Federico II” [name]
Objectives	
The primary objective of this study was to evaluate the proportion of successful treatments, defined as a 50% or greater reduction in the average daily duration of crying episodes after 28 days of treatment.
 
The secondary objectives were to evaluate the following variables:
 
Decrease from baseline in the number of crying episodes and in the persistence of colics at the end of the study (day 28).Decrease in the number of regurgitation and vomiting episodes.Number of respiratory, gastrointestinal, cutaneous and urinary infections during the study.Number of bowel movements and consistency of fecal mass.
Methodology	
This was a randomized, double-blind, placebo-controlled clinical study.
 
The study was conducted together with five family pediatricians practicing in the city of Naples. The pediatricians were asked to refer potentially eligible patients and to provide support, if necessary, to their parents. The objectives and procedures of the study were thoroughly presented to each pediatrician during a preliminary meeting held at the single trial center. During the study, the center was at the disposal of the pediatricians in case of need or clarification.
 
The Investigator was responsible for enrolling and evaluating the patients, as well as for completing the case report forms (CRF).
 
After the patient's parents had provided written informed consent, and once all eligibility criteria had been met, patients were required to follow a one-week pre-enrollment period during which fermented milk and nutritional supplements containing probiotics were prohibited. If after this period the diagnosis of infantile colic was confirmed, the patient was randomized in a 1:1 ratio to receive one of the two following products:
 
Bifidobacterium animalis subsp. lactis, BB-12®: 6 drops/day (which guaranteed 1 billion live cells) for 28 consecutive days.Placebo oil drops: 6 drops/day for 28 consecutive days. 
The patient's parents were provided with a diary and were instructed on how to complete it with data concerning the daily number and duration of crying episodes, the consistency of their baby's feces (according to the Bristol scale), and the daily number of bowel movements. Data was collected from these diaries at each weekly visit. Each patient was to undergo a total of 6 visits over a 5-week period.

Number of patients	The study population was made up of 80 children who met eligibility criteria.
Diagnosis and main criteria for inclusion	
Inclusion criteria
 
Exclusively breastfed babies of both sexes ≤ 7 weeks of age.Diagnosis of infantile colic according to Rome III Criteria.

	
3. Written informed consent of parents.
 
Exclusion criteria
 
 1. Weight at birth < 2500 g. 2. Gestational age < 37 weeks. 3. Apgar score at 5 minutes < 7. 4. Use of baby formulas. 5. Stunted growth/weight loss (< 100 g/week from birth to last reported weight). 6. Neurological diseases. 7. Confirmed or suspected food allergy. 8. Gastroesophageal reflux disease. 9. Intake of substances that alter intestinal microbiota (probiotics, prebiotics and antibiotics, gastric antacids) in the 2 weeks prior to enrollment. 10. Fever and/or infectious diseases in the 2 weeks prior to enrollment. 11. Current systemic infections. 12. History of congenital infection. 13. Chronic intestinal disease (cystic fibrosis or other forms of primary pancreatic insufficiency). 14. Primary or secondary gastrointestinal malformations (esophageal atresia, intestinal atresia, short bowel syndrome, malrotation). 15. Metabolic disease. 16. Genetic diseases and chromosomal abnormalities. 17. Primary or secondary immunodeficiency. 18. Insufficient reliability or presence of conditions that make the patient's compliance with the protocol unlikely. 19. Previous participation in this study.
Test product, dose and mode of administration	
 • Investigational treatment: dietary supplement containing Bifidobacterium (BB-12®) as active ingredient. Each 8 ml bottle with dropper contained 1 billion CFU per 6 drops. Dosage: 6 drops a day for 28 days. 
OR
 
 • Placebo indistinguishable from the investigational product in packaging, color, weight, smell and taste. Dosage: 6 drops a day for 28 days.
Criteria for evaluation	
Primary efficacy variable
 
The primary efficacy variable was the proportion of successful treatments, defined as a 50% or greater reduction in the average daily duration of crying episodes after 28 days of treatment.
 
Secondary efficacy variables
 
 • Decrease from baseline in the number of crying episodes and in the persistence of colics at the end of the study (day 28) • Decrease in the number of regurgitation and vomiting episodes • Number of respiratory, gastrointestinal, cutaneous and urinary infections during the study • Number of bowel movements • Consistency of fecal mass using the Bristol scale • Effects of BB-12 on intestinal microbiota • Variations of the intestinal production of innate immunity peptides (calprotectin, β defensin type 2, LL37) and short-chain fatty acids (butyrate e propionate) 
Safety variables
 
Safety was assessed based on the results of physical exams and on the incidence of adverse events (AE).

Statistical methods	
The following analysis sets were defined:
 
 • Per Protocol Set (PP): all randomized patients who completed the study without any significant protocol violation. • Intention to Treat Set (ITT): all randomized patients who received at least one dose of study treatment. • Safety Set: all randomized patients who received at least one dose of study treatment. 
Patients were analyzed according to the treatment received.

	
A patient who came back for Visit T2 was considered as having received at least one dose of study treatment.
 
The primary efficacy analysis was performed on the ITT population, and on the PP population as supportive. The secondary efficacy analysis was performed on the ITT population only. The safety analysis was performed on the Safety population.
 
Primary variable
 
Mean daily crying duration is described for each week by means of descriptive statistics for continuous data and was calculated on non-missing values; observations with values equal to zero were included in the computation. Mean change from baseline (mean of Week 1) was computed for each week.
 
The treatment success rate was evaluated in terms of the reduction of crying duration, comparing mean daily duration of the last Week (from T4 to T5) with that of Week 1 (from T0 to T1). Success was defined as a reduction $\geq 50\%$. The proportion of patients with successful outcomes in the two groups is summarized using descriptive statistics for categorical data and analyzed by means of a Chi-Square test.

Date and version	English version 1.0, 4 December 2019 – based on Protocol version 3, 16 May 2016 (document in Italian language)

## Statistical Analysis Plan

Sponsor: SOFAR

Protocol number: PSC-DS BIGI

## Statistical Analysis Plan

Sponsor: SOFAR

Protocol number: PSC-DS BIGI

### Document History

Status and Version	Release Date	Change Description	Reason/Comment
Draft Version 0.1	15 NOV 2017	N.A.	N.A.
Draft Version 0.2	16 NOV 2017	N.A.	Statistical revision.
Draft Version 0.3	02 JAN 2018	N.A.	Statistical revision.
Final Version 1.0	16 JAN 2018	First final release.	Sponsor's approval.

## Statistical Analysis Plan

Sponsor: SOFAR

Protocol number: PSC-DS BIGI

## Statistical Analysis Plan

Sponsor: SOFAR

Protocol number: PSC-DS BIGI

## Statistical Analysis Plan

Sponsor:

Protocol number:

### LIST OF ABBREVIATIONS

AE	Adverse Event
BB	Bifidobacterium animalis subsp. Lactis
CMED	Concomitant medication
CRF	Case Report Form
DNA	Deoxyribonucleic acid
g	grams
GCP	Good Clinical Practice
IC	Infantile Colic
ITT	Intent-To-Treat Population
NOPD	Non-Protocol Deviation
OTH	Other
PD	Protocol Deviation
PP	Per Protocol Population
SAE	Serious Adverse Event
SAF	Safety Population
sIgA	secretory IgA
WITH	Treatment withdrawal

	Statistical Analysis Plan
	Sponsor:
	Protocol number:

## 1. INTRODUCTION

### 1.1. CHANGES FROM THE STUDY PROTOCOL

Reduction of the number of cries from baseline to the end of study (after 28 days), presence of infantile colic at the end of study (after 28 days), reduction of the number of regurgitations and vomiting episodes will not be evaluated since information about these secondary objectives is not collected in the eCRF.

The analysis of Bifidobacterium BB-12® effect on gut microbiota, on the fecal production of peptides from innate immune system (Calprotectina,  $\beta$ -defensin 2, LL37) and on fecal short chain-fatty acids production (butyrate and propionate) will be provided by the center to Sponsor and reported in a separate document.

### 1.2. DISCLOSURE OF THE RESULTS

Dissemination of results will not be limited. No independent statisticians nor reviewers are foreseen.

## 2. STUDY OBJECTIVES

For the rationale of this study, please refer to Chapter 1.0 of the Study Protocol #3 dated 16 May 2016.

### 2.1. PRIMARY OBJECTIVE

The primary objective is to estimate the treatment's success rate, defined as the percentage of infants who have more than a 50% reduction in the average daily duration of cries after 28 treatment days from baseline.

### 2.2. SECONDARY OBJECTIVES

- Reduction of the number of cries from baseline to the end of study (after 28 days) and presence of infantile colic at the end of study (after 28 days);
- reduction of the number of regurgitations and vomiting episodes;
- number of infections of the respiratory system, gastrointestinal system, urinary system or skin during the study period;
- evacuative frequency;
- consistency of the fecal mass;

	Statistical Analysis Plan
	Sponsor:
	Protocol number:

- Bifidobacterium BB-12® effect on gut microbiota, on the fecal production of peptides from innate immune system (Calprotectina,  $\beta$ -defensin 2, LL37) and on fecal short-chain fatty acids production (butyrate and propionate).

### **2.3. EXPLORATORY OBJECTIVES**

Not Applicable.

## **3. BACKGROUND AND RATIONALE**

### **3.1. STUDY DESIGN**

This is a prospective randomized double blind placebo controlled clinical trial.

Enrolled patients are treated with a dietary supplement containing Bifidobacterium subsp.lactis animalis BB-12® (Bifidolactis Infant) or Placebo, provided free of charge by SOFAR S.p.A.

The trial is conducted at the Department of Translational Medical Sciences, “Federico II” University of Naples as the sole participating center (Principal Investigator: [name] [name]).

### **3.2. TREATMENT GROUPS AND RANDOMIZATION**

Enrolled infants are randomized at T1 to Bifidobacterium BB-12® or Placebo.

Randomization is done according to a randomization list obtained by a specific software and provided by the Coordinator Center.

The treatment regimen can be summarized as follows:

- Group I: patients who take Bifidobacterium BB-12® (Bifidolactis Infant), 6 drops a day (guaranteeing a billion of living cells) for 28 consecutive days;
- Group II: patients who take Bifidolactis Infant Placebo 6 drops a day for 28 consecutive days.

### **3.3. STUDY POPULATION**

#### **Inclusion criteria**

Patients are included in the study if they meet all the following criteria:

- Exclusively breastfed healthy infants of both sexes, aged  $\leq$  7 weeks.
- Diagnosis of IC according to Rome III criteria.
- Written informed consent of the parent/tutor.

#### **Exclusion criteria**

	Statistical Analysis Plan
	Sponsor:
	Protocol number:

Patients are excluded from this study if they meet any of the following criteria:

- Birth weight < 2500 g.
- Gestational age < 37 weeks.
- APGAR 5 minutes < 7.
- Formula feeding.
- Stunting/loss of weight (< 100 g/weeks from birth to the last reported weight).
- Neurological diseases.
- Known or suspected food allergy.
- Gastroesophageal reflux disease.
- Use of substances that alter gut microbiota (probiotics, prebiotics, antibiotics, gastric acidity inhibitors) in the last 2 weeks prior the enrollment.
- History of fever and/or infectious diseases in the last 2 weeks prior to enrollment.
- Ongoing systemic infections.
- History of congenital infections.
- Chronic intestinal diseases (cystic fibrosis or other forms of primitive pancreatic insufficiency)
- Primitive or secondary malformations of the gastrointestinal tract (such as esophageal atresia, intestinal atresia, short bowel syndrome, malrotation).
- Metabolic diseases.
- Genetic diseases and chromosomal abnormalities.
- Primary or secondary immunodeficiencies.
- Not sufficient reliability or presence of conditions that may result in non-compliance/adherence of the patient to the Protocol.
- Previous participation in this study.

### **3.4. STUDY DRUG AND DOSING**

Parents/tutors receive two vials of dietary supplement Bifidobacterium BB-12® (Bifidolactis Infant) or Bifidolactis Infant Placebo for the entire treatment period (28 days); each vial is provided together with a dispenser and contains drops for 21 days.

Bifidolactis Infant and Placebo are packaged in indistinguishable boxes.

One vial of the investigational drug contains 6 ml and one billion of living cells.

## Statistical Analysis Plan

Sponsor:

Protocol number:

The vial contains sunflower oil (*Helianthus annus* L.) and the cap contains *Bifidobacterium BB-12®* (*Bifidobacterium animalis* subsp. *Lactis*, strain deposited DSM 15954) and maltodextrin.

An adequate supply of product is provided free of charge by SOFAR S.p.A.

Reference samples of *Bifidolactis* Infant and Placebo are deposited at the SOFAR S.p.A. quality control department.

Infants receive 6 drops a day; drops should be dosed on a spoon and mixed with mother's milk.

### 3.5. PROHIBITED MEDICATIONS

Probiotics/prebiotics/synbiotics and other anti-colic drugs should be avoided during the study.

### 3.6. SAMPLE SIZE

According to the results of a previous trial that looked at a probiotic's effect on infants with CI, it is estimated that when the sample size in each group is 33, the study will have 80% power to detect an absolute difference of 35% in the treatment success rate (15% in the Placebo group and 50% in the treatment group) with a 0,05 alpha level.

The number of infants that will be included in the study is 80, with a dropout rate expected for a maximum of 20%.

### 3.7. SCHEDULE OF TIME AND EVENTS

The total duration of the study is established in 5 weeks for each infant.

All infants should enter a 1 week run-in period during which probiotic fermented milk, probiotic dietary supplements and prebiotic dietary supplements should be avoided. After this period, if the diagnosis of CI is confirmed, the infant is eligible for the study and is randomized to investigational treatment or Placebo.

During the first visit (T0), the Investigator assesses inclusion/exclusion criteria and tells parents of the study objective and design.

After having parents/tutor written informed consent, the Investigator evaluates family medical history and the infant's clinical condition, and instructs parents on how to record data in the diary about: number and duration of daily cries, fecal consistency and evacuative frequency for the subsequent 7 days.

After 7 days (T1) a new visit is planned; if the diagnosis of CI is confirmed, a fecal sample is collected and the infant is assigned to *Bifidobacterium BB-12®* or to Placebo, according to the randomization list. Infants should take treatment for 4 weeks.

The Investigator tells parents the product daily dose and instructs them on how to administer the product accurately.

All infants are examined weekly by the Investigator for 28 days from randomization.

## Statistical Analysis Plan

Sponsor:

Protocol number:

At each visit (T2, T3, T4, T5) the infant's clinical conditions are recorded, diary completeness is checked and parents/tutor receive a new dairy for data collection.

All anthropometric data are collected at T0, T1 and T5.

At T1 and T5, a fecal sample (3 g) is collected for each infant to evaluate:  $\beta$ -defensin 2, LL37, Calprotectina (ELISA method), sIgA, intestinal microbiota (through 16SrRNA amplification and quantification and DNA microarrays) and short-chain fatty acids (butyrate and propionate) through gas-chromatography.

Six visits are planned during the study according to the flow chart shown in Table 2.6-1:

Table 2.6-1: Flow Chart

Visit	T0	T1	T2	T3	T4	T5
Days	1	7	14	21	28	35
Inclusion / Exclusion criteria	X	X				
Written Informed Consent	X					
Anthropometric data	X	X				X
Randomization		X				
Investigational treatment		X	X	X	X	
Medical history	X					
Clinical data	X	X	X	X	X	X
Physical examination	X	X	X	X	X	X
Diary completeness check		X	X	X	X	X
Fecal samples		X				X

## 4. ANALYSIS POPULATIONS

The following analysis sets are defined:

- Per Protocol Set (PP): all randomized patients who complete the study without any significant protocol violation.
- Intention to Treat Set (ITT): all randomized patients who receive at least one dose of study treatment. Following the intent-to-treat (ITT) principle patients will be analyzed according to the treatment they have been assigned to at the randomization visit.
- Safety Set: all randomized patients who receive at least one dose of study treatment. Patients will be analyzed according to the actual treatment received.

A patient who receives at least one dose of study treatment will be defined as a patient who comes back at Visit T2.

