**Table 3-2: List of non-protocol deviations**

Deviation code	Description	Exclusion from analysis population
NOPD1	Patient who was not randomized	PP/ITT/Safety
NOPD2	Randomized patient who did not have receive at least one dose of study treatment	PP/ITT/Safety

\* NOPDs = Non-protocol deviations

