### **6.2. STUDY PATIENTS**

#### **Patient Disposition**

A complete description of patient disposition will be provided on the enrolled patients overall and by treatment group. The number and percentage of patients entered at each visit, as well as the number of patients who completed and discontinued the study will be provided with the reasons for discontinuation. A complete description of the number of protocol violators and the number of patients per deviation will be summarized in the Patient Validation Document.

The numerosness of the analysis population will be described overall and by treatment group and the reason excluding the patient from any analysis population will be provided.

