### 6.4. DRUG EXPOSURE AND TREATMENT COMPLIANCE

	Statistical Analysis Plan
	Sponsor:
	Protocol number:

Exposure will be computed as the time in days elapsed from the date of the first study drug administration (Visit T1) to the date of the last study drug administration (if applicable) or to the date of the day before Visit T5.

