## Statistical Analysis Plan

Sponsor:

Protocol number:

Moreover, in order to compare the two groups of patients, a t-test on the change of weekly mean of cries at last Week will be performed. In case of data not normally distributed, a Wilcoxon/Mann-Whitney test will be used.

- Number of infections of the respiratory system, gastrointestinal system, urinary system or skin during the study period.

Number of infections will be described on the ITT population, even if infections are defined using safety parameter. In fact, an infection will be defined as an Adverse Event with SOC equal to "Infections and Infestations".

The frequency and proportion of patients who reported at least one infection will be summarized and presented by category, System Organ Class and Preferred Term.

- Evacutive frequency

Frequency and consistency of stools are collected daily in the diary.

Stool frequency will be evaluated as the mean of total daily stools reported per week. Mean changes from baseline (i.e. mean of the first Week) to the mean of the selected week will be analyzed.

Summary statistics of mean stool frequency per week will be provided by means of descriptive statistics for continuous data.

- Consistency of the fecal mass

Stool consistency will be evaluated as the number and the proportion of patients who reported at least one stool sample of each type per week, according to Bristol scale. Patients could report more than one stool consistency per day (according to the number of daily stools): all the information collected will be analyzed.

Other data from patients' diary will be analyzed:

- Infant's mood

Infant's mood (calm, asleep, agitated, irritable) is collected daily in the diary and will be evaluated as the number and the proportion of infants who reported at least one mood of each type per week.

- Infant's sleep

Duration of sleep (in minutes) will be collected daily in the diary during the entire study period. The average daily duration will be defined as the mean duration of all sleeps during the day (i.e. sum of episodes' duration/number of sleeps during the day).

Weekly mean will be defined as the mean of the calculated average daily durations during the selected week and will be described by means of descriptive statistics for

	Statistical Analysis Plan
	Sponsor:
	Protocol number:

continuous data. Mean changes from baseline (i.e. mean of the first Week) to the mean of the selected week will be analyzed too.

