### **6.6. SAFETY EVALUATION**

Safety data will be summarized by treatment on the Safety population.

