#### **6.6.1. Adverse Events**

The incidence of Adverse Events (AEs) and Serious Adverse Events (SAEs) recorded during all the study will be presented. Treatment-emergent events will be considered those AEs with an onset date after the initiation of treatment.

Non-treatment emergent adverse events (i.e. events occurring between T0 and T1) will be listed separately.

Tables reporting a general summary of AEs will be produced by treatment group specifying the number of total events and the absolute and relative frequency of patients with AEs. As

	Statistical Analysis Plan
	Sponsor:
	Protocol number:

a patient may have more than one AE, the total number of AEs could be greater than the total number of patients.

Absolute and relative frequency of patients with drug related AEs, severe AEs, SAEs, AEs with an outcome of death, AEs leading to permanent discontinuation of treatment, AEs leading to temporarily interruption, AEs leading to hospitalization/prolonged hospitalization will be also reported.

Drug-related AEs will be the AEs with causality equal to "Probably", "Possibly" and "NA"; if the relationship to study drug is unknown or missing, the AE will be drug related as well.

AEs will be tabulated by System Organ Class, Preferred Term and severity. The absolute and relative frequency of patients who have experienced each type of event will be presented; if the same patient reported more than one occurrence of the same AE with different intensity, no selection of the one with the worst intensity will be adopted.

SAEs will be summarized similarly.

All serious AEs, study drug related AEs, AEs with an outcome of death, AEs leading to permanent discontinuation of treatment will be listed with all their details.

Relative days, defined as days elapsed from the treatment start to the onset date of the event, will be computed.

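### Defining a dosed infant as one who returns at T2 removes early leavers from the Safety set, and their treatment-emergent events from the AE and SAE tables

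*SAP*

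**What the plan says.** SAP section 4 builds the Safety and ITT sets from randomised infants with one or more doses. It then gives the working test for dosing: "A patient who receives at least one dose of study treatment will be defined as a patient who comes back at Visit T2". The Statistical methods part of the protocol synopsis has the same rule, so the two documents agree.

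An infant who fails the test falls under code NOPD2 in SAP Table 3-2, "Randomized patient who did not have receive at least one dose of study treatment", which removes the infant from the PP, ITT and Safety sets. Section 4 also bars patients who do not meet the set criteria from all analyses.

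Other sections start treatment a week earlier than T2. Section 6.4 counts exposure from "the date of the first study drug administration (Visit T1"), and the flow chart in section 3.7 puts T1 at day 7 and T2 at day 14. Section 6.6.1 follows the true start of treatment: "Treatment-emergent events will be considered those AEs with an onset date after the initiation of treatment".

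The reporting rule in section 6.6 is: "Safety data will be summarized by treatment on the Safety population". The infection endpoint in section 6.5.3 is built from adverse events but uses the other set: "Number of infections will be described on the ITT population, even if infections are defined using safety parameter".

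**The concern.** Attendance at T2 is a post-randomisation event that treatment can affect. A family that leaves in the first treatment week because of an adverse event is the case a safety table most needs to show, and it is the case this rule removes. The SAP also conflicts with itself: an event between T1 and T2 in such an infant is treatment-emergent under section 6.6.1, while the infant is untreated under section 4 and Table 3-2.

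The tables of SAEs and of AEs leading to discontinuation could therefore show zero for an arm in which such an event occurred. The disposition table, which covers enrolled patients, could at the same time show a discontinuation for that reason.

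Read literally, the rule misclassifies in two more ways. An infant who takes product, misses T2 and attends T3 counts as never dosed. An infant who attends T2 having taken nothing counts as dosed. An infant who stops product in the first week but attends T2 is classified correctly.

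**Working it through.** The plan attaches no figure to this rule, so the check follows the definitions and then illustrates the size.

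**Following one infant through the plan**

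1. Randomised and started on product at T1, day 7 (SAP 3.7 and 6.4).
2. Has an adverse event between day 7 and day 14. Onset is after treatment start, so it is treatment-emergent (SAP 6.6.1).
3. Does not attend T2, so is deemed to have had no dose (SAP 4; protocol synopsis).
4. Coded NOPD2 and excluded from PP, ITT and Safety (SAP Table 3-2).
5. AE summaries use the Safety population (SAP 6.6), so the event is not tabulated. If it is an infection, it is also absent from the infection endpoint on the ITT set (SAP 6.5.3).
6. Nothing in either document brings the infant back. The only separate AE listing by timing is for events between T0 and T1, which does not apply here.

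**Length of the gap**

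T2 minus T1 = 14 − 7 = 7 days. 7/28 = 25% of the treatment course.

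**Illustration of size**

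Inputs: 80 infants (SAP 3.6) randomised 1:1 (protocol synopsis) give 40 per arm.

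Assumptions, not in the documents: all 40 are dosed; k infants in one arm leave before T2, each because of an AE; no other infant in that arm has an AE discontinuation.

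The rate on all dosed infants is k/40. The rate the SAP would tabulate is 0/(40 − k). Intervals are exact (Clopper-Pearson) 95%.

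| k | All dosed infants | SAP Safety set |
|---|---|---|
| 1 | 1/40 = 2.5% (0.06 to 13.16) | 0/39 = 0% (0 to 9.03) |
| 2 | 2/40 = 5.0% (0.61 to 16.92) | 0/38 = 0% (0 to 9.25) |
| 4 | 4/40 = 10.0% (2.79 to 23.66) | 0/36 = 0% (0 to 9.74) |

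If other infants in the arm also have such events, the table does not reach zero but is still too low. With one affected infant lost, 2/40 (5.0%) becomes 1/39 (2.6%), and 4/40 (10.0%) becomes 3/39 (7.7%).

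**Bound on early loss**

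The planned maximum dropout is 20% (SAP 3.6), or 0.20 × 40 = 8 per arm. If all of it fell before T2, the Safety set would be 32 in that arm. This is an upper limit, not an expectation.

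**The case against.** The strongest reply is that the loss would not be silent. Section 6.2 reports disposition on enrolled patients by arm, where "the number of patients who completed and discontinued the study will be provided with the reasons for discontinuation", and it also requires the reason for each exclusion from an analysis set. Section 4 has set assignment summarised before database lock. Section 6.6.1 states that serious, drug-related and fatal events and "AEs leading to permanent discontinuation of treatment will be listed with all their details". A careful reader could find the excluded infant and see why the AE table and the disposition table differ.

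This stands in part. These provisions make it less likely that the infant goes unnoticed, and tables on differently labelled populations need not contradict each other. They do not put the event back into any AE count or restore the denominator. The listing sentence names no population, and the section 4 bar on all analyses leaves open whether an excluded infant would be listed.

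It can also be said that T2 return is a practical proxy, because neither document describes a dispensing log or daily dose record. That explains the rule but not the direction of its error: for safety, an infant given product should be presumed exposed, and the proxy presumes the opposite. Section 6.4 already takes T1 as first administration and foresees a last-administration date where applicable, so some dosing information is expected. A presumption of exposure has its own cost, since it keeps infants with unknown dosing and follow-up in the denominator and may dilute AE rates slightly.

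Finally, the number affected may be zero, and four AE leavers in one arm before T2 would be half of that arm's planned maximum dropout of 8. Both points are right. They limit the expected size but do not make the rule correct.

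**Conclusion.** The concern holds. Applied as written, the plan drops a treated infant who does not return at T2 from the Safety set and leaves that infant's treatment-emergent events out of the summary tables and the infection endpoint.

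The figure that comes from the documents is the gap of 7 of 28 treatment days. The number of infants affected is not given. The falls to 0/39 and 0/36 rest on the assumed 1 to 4 AE leavers in an arm of 40 and on no later AE discontinuation in that arm. With arms of about 40, one infant can decide whether a row reads zero.

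No effect on the primary success rate is claimed from this rule alone. SAP 6.1 computes percentages on non-missing data by default and marks missing-data and drop-out handling as not applicable, so an infant without diary data for the last week would leave that percentage anyway. The change should be made, but the primary result does not depend on it.

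**What to change.** - Delete the T2-return definition from SAP section 4 and from the protocol synopsis.
- Define the Safety set as all randomised infants given product at T1, unless records or the parents indicate that no dose was taken, analysed by treatment received.
- Apply NOPD2 on that basis and not on attendance.
- State in section 6.6.1 that AE listings include every randomised infant.
- Define ITT membership by randomisation, or at least not by T2 attendance. This alters the primary success rate only if the SAP also says how infants without last-week diary data are counted, for example as non-successes, so that rule should be stated with it. The Safety-set correction does not depend on the ITT change.

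The cost is wording in both documents plus, for each infant who did not return at T2, a check of available records or parent report on whether any dose was taken. No new visit or measurement is needed.
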